1.0 Objectives

Objective

The objective of the study is to establish a prospective disease registry for chronic recurrent multifocal osteomyelitis (CRMO)/chronic nonbacterial osteomyelitis (CNO) in order to investigate the natural history of the disease and the responses of patients to different clinical managements over 5 years.

Aims

Aim 1: To determine the clinical characteristics that are related to prognosis

Aim 2: To compare the effectiveness of various clinical managements in practice setting.

Aim 3: To characterize the long-term outcome of CNO

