outcomes of CNO remains unknown due to the lack of prospective study. It has been estimated that at least 50% of CNO patients continue to need medications for CNO during adulthood. Our study will collect the clinical data for up to 20 years and provide valuable data to characterize the long-term outcomes.

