3.0 Inclusion and Exclusion Criteria

Potential subjects will be identified by electronic medical record searches, clinic schedules, inpatient lists, and word of mouth recommendation. A member of the study team will review the potential subject's medical records to confirm diagnosis, language, and care plan. If eligible, the caregiver and subject will be approached for participation. Eligibility will be confirmed with the caregiver verbally prior to obtaining informed consent.

Inclusion Criteria

- Presence of bone edema on STIR or T2 fat saturation sequence on MRI within 12 weeks of enrollment (optional)
- Whole body imaging evaluation (either WB MRI or bone scintigraphy) is optional
- Bone biopsy to exclude infection or malignancy when indicated

Exclusion Criteria

- History of or current malignancy
- Current infectious osteomyelitis
- Contraindication to the selected treatment agent

Adults who are unable to consent and lack a legal guardian, wards of the state, and prisoners will be excluded.

Caregivers will be reporting about the subject's medical history therefore they are not considered study subjects.

As this is a multicenter international study, sites will use local language such as Turkish, German, Italian, etc.

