7.0 Study Timelines

Study participation will commence when informed consent is signed and ends 20 years thereafter or sooner, if subject transitions to other practices.

We expect to approach all eligible subjects for participation therefore; recruitment and enrollment will be ongoing.

At this time, we plan to analyze the data periodically per the study aims above. Additional analyses may be added as IRB modifications in the future. Results of deidentified analyses may be shared with the clinical program team for quality improvement.

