8.0 Study Endpoints

Primary Endpoint: Determine the effectiveness of commonly used medications in SOP for patients with CNO.

Clinical, laboratory and imaging results as well as PROs will be collected at each clinical visit after enrollment. Enrolled subjects will be stratified based on their past disease course, past treatment. Response to medication will be calculated based on previously described by Beck et al.⁵ and Zhao et al.² at clinical visits prior to and after starting a new medication for comparison. Clinical disease activity score (CDAS) comprised of patient pain (0-10), patient global disease activity per report (0-10), clinical lesion count by physician, will be used to determine response. >=50% of reduction of CDAS is defined as favorable response.

Secondary Endpoint: Determine the risk factors for patients with NSAID-refractory CNO.

Patients will be classified as NSAID responders (significant improvement of pain, focal exam, ESR, CRP, imaging within 6 months of NSAIDs treatment), NSAID non-responders (requiring >6 weeks of systemic glucocorticoid, disease modifying anti rheumatic drugs, TNF inhibitors, bisphosphonate) based on treating physician's assessment. Baseline demographic, clinical, laboratory, imaging results will be compared between two groups and odds ratio will be calculated. There is no safety endpoint because it is an observational study that does not pose any risk to subjects.

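### For Aims 1 and 3, results over 5 years from enrolment would mix disease stages and probably over-represent persistent CNO; the plan should time from diagnosis with delayed entry

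*Protocol*

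**What the plan says.** Protocol 1.0 gives the objective as "to investigate the natural history of the disease and the responses of patients to different clinical managements over 5 years" but no starting point for the 5 years. Aim 1 concerns characteristics related to prognosis and Aim 3 the long-term outcome.

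The one clock in the document is in Section 7.0: "Study participation will commence when informed consent is signed and ends 20 years thereafter or sooner, if subject transitions to other practices". Section 2.0 has the same horizon: "Our study will collect the clinical data for up to 20 years".

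On entry, Section 3.0 says: "Potential subjects will be identified by electronic medical record searches, clinic schedules, inpatient lists, and word of mouth recommendation". No criterion concerns time since onset or diagnosis. The only time window, an MRI finding no more than 12 weeks old at enrolment, is marked optional and concerns current activity. Section 7.0 adds: "We expect to approach all eligible subjects for participation therefore; recruitment and enrollment will be ongoing".

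Long-standing patients are plainly expected. Section 8.0, under the primary (effectiveness) endpoint, says "Enrolled subjects will be stratified based on their past disease course, past treatment", and the Section 11.0 model adjusts for past medication, number of lesions, age and gender. Disease duration is not listed. Section 9.0 permits, but does not require, chart review of visits before consent.

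**The concern.** Natural history and prognosis are questions about what happens after a disease starts. A child in the first month of CNO and an adolescent in the seventh year can both consent on the same day. If both are followed for 5 years from that day, the pooled result describes neither the first 5 years of CNO nor any other fixed stretch of it.

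The second issue is who is there to be enrolled. Section 2.0 describes a range from limited single-site disease to chronically active multifocal disease. A patient whose disease settled and who left care before the registry opened is harder to find and enrol than one still attending. Among existing patients, those with lasting disease are then over-represented (length-biased sampling, or left truncation).

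At stake is the reading of the results. Section 2.0 says long-term outcomes are unknown for lack of prospective study, and it hopes to validate published risk factors for severe disease. Rates of remission or continuing medication from a mixed cohort could be taken as the course of CNO from its start, and would probably look too pessimistic.

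**Working it through.** The protocol gives no rate, precision or power calculation for Aims 1 or 3, and the ceiling of 2000 subjects in Section 4.0 has no inputs, so there is no figure to reproduce. The numbers below are illustrations.

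**1. Composition of the cohort**

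Inputs:
- *p*, share with persistent disease at onset: assumed 50% or 30%. Section 2.0 cites an estimate that at least half still need medication in adulthood; that only suggests the order of magnitude.
- *R*, mean time in care of persistent relative to resolving patients: not in the documents; assumed 1 to 5.
- *f*, fraction of enrolment made up of existing patients: not in the documents; shown at 1 and 0.5.

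Share persistent among existing patients = pR / (pR + 1 − p). Share in the whole cohort = f × that + (1 − f) × p.

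Example, p = 0.5 and R = 3: 1.5 / (1.5 + 0.5) = 75%; with f = 0.5, 0.5 × 75% + 0.5 × 50% = 63%.

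| p | R | all existing (f = 1) | half existing (f = 0.5) |
|---|---|---|---|
| 50% | 1 | 50% | 50% |
| 50% | 2 | 67% | 58% |
| 50% | 3 | 75% | 63% |
| 50% | 5 | 83% | 67% |
| 30% | 1 | 30% | 30% |
| 30% | 2 | 46% | 38% |
| 30% | 3 | 56% | 43% |
| 30% | 5 | 68% | 49% |

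The direction follows whenever R exceeds 1. At R = 1 nothing is distorted.

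**2. Effect on a 5-year figure**

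Assume onset spread evenly over the past 20 years, active disease lasting on average 10 years in half the patients and 2 years in the other half (exponential), and patients in care while active.

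- Truly active 5 years after onset: 0.5 × e^(−0.5) + 0.5 × e^(−2.5) = 0.303 + 0.041 = 34%.
- Persistent share among existing patients: 10(1 − e^(−2)) = 8.65 against 2(1 − e^(−10)) = 2.00, so 8.65 / 10.65 = 81%.
- Active 5 years after consent, existing patients: 0.812 × 0.607 + 0.188 × 0.082 = 51%.
- Half new, half existing: 0.5 × 51% + 0.5 × 34% = about 43%.

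A simulation of 2,000,000 patients agrees. It puts median disease duration at consent for existing patients at 4.4 years (interquartile range 1.7 to 9.2), so 5 years from consent ends at a median of about 9.4 years of disease.

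**3. Moving time zero alone does not cure it**

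In the same simulation, counting from onset but treating existing patients as if observed from onset makes 78% appear active beyond 5 years, against the true 34%. Those who resolved earlier could not be enrolled, and the calculation ignores this. With delayed entry, each patient counts only from the disease duration reached at consent. If entry time is unrelated to later course, the risk set at each duration then represents patients still active at that duration, and the 34% is recovered.

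**The case against.** The strongest reply is that Section 7.0 defines when participation starts, not the time zero of any analysis, and a statistical analysis plan not available here could count from diagnosis. That stands: a reader might infer that the protocol fixes analysis time at consent, and it does not. What remains is that consent is the only clock stated, the 5 years have no origin, and step 3 shows that choosing diagnosis without delayed entry can be worse.

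A reader might also infer that recovered patients have almost no chance of being approached. The text does not support that. Record searches head the list of sources in Section 3.0, Section 23.0 allows contact by phone, mail, email and social media, and Section 29.0 waives consent for adults who have left the lead site. These lessen the selection. They do not remove it: ordinary follow-up data come from scheduled clinic visits, Section 29.0 itself says departed patients may be unreachable, and the waiver needs age 18 or over and a documented transition, at one site.

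Other points also hold in part. With ongoing enrolment the existing patients are a backlog, so their share should fall with time; selection against early recovery applies to them, not to newly diagnosed enrollees. Retrospective review can supply dates and early course, but it is optional and adds no one who was never enrolled. Past medication and age may partly stand in for duration. The secondary endpoint, NSAID response within 6 months of treatment, is anchored to treatment rather than consent, and its odds ratio is not shifted merely by enrolling more non-responders if selection depends on response alone.

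Finally, confining the main estimate to patients enrolled near diagnosis would discard information in a rare disease. That objection is sound.

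**Conclusion.** The concern holds for Aims 1 and 3 in a limited form. Entry is open to any disease duration, the only stated clock runs from consent, and duration is not a listed covariate. Five-year estimates from enrolment would therefore mix disease stages; that follows from the text. Over-representation of persistent disease is a probable inference that rests on such patients staying in care longer.

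Its size is unknown. The illustrations run from no distortion (R = 1) to 83% persistent against a true 50% (R = 5, existing patients only), and none of these inputs comes from registry data. They should not be read as an estimate of bias in this registry. Aim 2 is less affected, because response is anchored to starting a new medication.

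This is worth correcting: the remedy is standard and cheap, and the mitigations in the protocol do not remove left truncation.

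**What to change.** For Aims 1 and 3:

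- Record the date of diagnosis (or of first symptoms) for every patient, and use it as time zero.
- Let patients enter the risk set at consent. In a first-event analysis, leave out those whose event came before consent. Patients included by waiver have no consent date; report them separately.
- Add disease duration at enrolment as a covariate or stratum. This also gives a check on the delayed-entry assumption that entry time is unrelated to later course.
- Pre-specify a sensitivity or parallel analysis of patients enrolled within a fixed window of diagnosis, for example 12 months, not as the sole main estimate.
- State in Section 1.0 whether the 5 years run from diagnosis or from enrolment, and how they relate to the 20-year follow-up.

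Enrolment and Aim 2 stay as they are, and no visits are added. The cost is some extra analysis work and less precision early after diagnosis, where few existing patients contribute. Because retrospective review is now optional, the diagnosis date would have to become a required item.

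Delayed entry does not correct recruitment that favours patients in flare at a given disease duration, so that limitation should be reported.

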2.0 Background

Chronic nonbacterial osteomyelitis (CNO) is an autoinflammatory bone disease that mainly affects children and adolescents. Clinical presentations range from mild and sometimes limited unifocal disease to severe, chronically active or recurrent inflammation of multiple bones. The latter is referred to as chronic recurrent multifocal osteomyelitis (CRMO). Here we will use the term "CNO" to refer to the entire spectrum of this disease. CNO can be complicated by vertebral compression fractures, kyphosis, and leg length discrepancy when it is not recognized early or treated adequately. The diagnosis of CNO is made by excluding alternatives in the differential diagnosis including malignancy (leukemia, lymphoma, and primary or metastatic bone tumors), Langerhans cell histiocytosis, and infection. Clinical assessment in conjunction with serum inflammatory parameters and imaging studies, particularly magnetic resonance imaging (MRI), are crucial for the diagnosis and monitoring of disease activity of CNO¹.

Because of significant variation in clinical treatment practices among pediatric rheumatologists, standardized treatment regimens (consensus treatment plans, CTPs) have been developed within the Childhood Arthritis and Rheumatology Research Alliance (CARRA), a North American organization comprised of pediatric rheumatologists and researchers, for CNO patients with an NSAID-refractory course and/or with active spinal lesions². These CTPs provide an opportunity for pediatric rheumatologists to conduct comparative effectiveness research on CNO through prospective data collection. CRMO/CNO workgroup is comprised of pediatric rheumatologists from North America as well as international colleagues who are interested in collaborating in CNO research. Furthermore, risk factors of severe disease have been described by Wipff et al. based on a large retrospective cohort study³. Their results may be validated by an independent prospective cohort study. To date, there has been only one prospective study on CNO since its first description in 1972⁴. Therefore, we propose to establish this international registry of patients with CNO to accomplish above goals. Long-term

outcomes of CNO remains unknown due to the lack of prospective study. It has been estimated that at least 50% of CNO patients continue to need medications for CNO during adulthood. Our study will collect the clinical data for up to 20 years and provide valuable data to characterize the long-term outcomes.

3.0 Inclusion and Exclusion Criteria

Potential subjects will be identified by electronic medical record searches, clinic schedules, inpatient lists, and word of mouth recommendation. A member of the study team will review the potential subject's medical records to confirm diagnosis, language, and care plan. If eligible, the caregiver and subject will be approached for participation. Eligibility will be confirmed with the caregiver verbally prior to obtaining informed consent.

Inclusion Criteria

- Presence of bone edema on STIR or T2 fat saturation sequence on MRI within 12 weeks of enrollment (optional)
- Whole body imaging evaluation (either WB MRI or bone scintigraphy) is optional
- Bone biopsy to exclude infection or malignancy when indicated

Exclusion Criteria

- History of or current malignancy
- Current infectious osteomyelitis
- Contraindication to the selected treatment agent

Adults who are unable to consent and lack a legal guardian, wards of the state, and prisoners will be excluded.

Caregivers will be reporting about the subject's medical history therefore they are not considered study subjects.

As this is a multicenter international study, sites will use local language such as Turkish, German, Italian, etc.

4.0 Study-Wide Number of Subjects

This is a multicenter registry with Seattle Children's being the lead site. Due to the rarity of CRMO, we expect to accrue up to 2000 subjects at all sites that gain IRB approval.

5.0 Study-Wide Recruitment Methods

Potential subjects at other sites may be enrolled in a similar manner as those enrolled at Seattle Children's Hospital with subjects being identified by electronic medical record searches, clinic schedules, inpatient lists, and word of mouth recommendation. If local

sites allow, flyers and social media may also be used. The coordinating center, however, does not have control over the recruitment methods used at the participating sites.

6.0 Multi-Site Research

[name] is the study lead PI and is responsible for verifying that all sites have local IRB approval prior to study work being done. [name] and/or his study team will be in charge of sending the most current versions of all regulatory documents to the sites once they are approved by Seattle Children's IRB.

[name] will ensure that any study modifications are appropriately justified and receive Seattle Children's IRB approval prior to being implemented. Any study modifications and/or study closure instructions will be outlined in an email that will be sent to all sites. Emails will be sent using the "Delivery Receipt" to ensure that sites receive the emails. Sites will be asked to reply to the email ensuring that they understand the modifications. If there are questions, [name] or the study team will be made available for a telephone call.

In addition, [name] and his study team may plan to hold monthly phone calls to discuss study progress and interim results with the other sites. If a problem arises at sites, [name] and the site PI will communicate via email and/or phone in order to resolve it.

7.0 Study Timelines

Study participation will commence when informed consent is signed and ends 20 years thereafter or sooner, if subject transitions to other practices.

We expect to approach all eligible subjects for participation therefore; recruitment and enrollment will be ongoing.

At this time, we plan to analyze the data periodically per the study aims above. Additional analyses may be added as IRB modifications in the future. Results of deidentified analyses may be shared with the clinical program team for quality improvement.

8.0 Study Endpoints

Primary Endpoint: Determine the effectiveness of commonly used medications in SOP for patients with CNO.

Clinical, laboratory and imaging results as well as PROs will be collected at each clinical visit after enrollment. Enrolled subjects will be stratified based on their past disease course, past treatment. Response to medication will be calculated based on previously described by Beck et al.⁵ and Zhao et al.² at clinical visits prior to and after starting a new medication for comparison. Clinical disease activity score (CDAS) comprised of patient pain (0-10), patient global disease activity per report (0-10), clinical lesion count by physician, will be used to determine response. >=50% of reduction of CDAS is defined as favorable response.

Secondary Endpoint: Determine the risk factors for patients with NSAID-refractory CNO.

Patients will be classified as NSAID responders (significant improvement of pain, focal exam, ESR, CRP, imaging within 6 months of NSAIDs treatment), NSAID non-responders (requiring >6 weeks of systemic glucocorticoid, disease modifying anti rheumatic drugs, TNF inhibitors, bisphosphonate) based on treating physician's assessment. Baseline demographic, clinical, laboratory, imaging results will be compared between two groups and odds ratio will be calculated. There is no safety endpoint because it is an observational study that does not pose any risk to subjects.

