9.0 Procedures Involved

This is a multicenter registry which involves the following procedures:

- Prospective Chart review: will be performed to collect data when subjects and caregivers come to Seattle Children's Hospital or a participating site for a scheduled clinic visit.
- Retrospective Chart review: may also be performed for visits which occurred prior to informed consent, as long as these are already available in the medical record.
- Safety Procedures: The required portions of the study are limited to ongoing review of the subject's medical record, and therefore carry very minimal risk.
- Questionnaires: Subject's will be asked several questions that are not in their medical chart such as their demographics, complete medical history, medications, etc.

No additional visits to the hospital will be requested as all study-related questionnaires will be done when subject comes to the site for a standard of care scheduled clinic visits. At Seattle Children's, subjects typically come to clinic at the every 3-12 months interval after diagnosis, however, this may vary at participating sites.

Access to standard care will not be delayed or precluded by participation in this registry.

The Case Report Forms should be filled out by the participating site study team and data transcribed into the electronic database in a timely manner. Each site will be able to view their own data, while Seattle Children's (coordinating center) will be able to view all of the uploaded limited data, which includes date of birth, partial postal close, date of death, and gender. If needed, for quality review, sites may be asked to send a scan of their completed Case Report Forms to the coordinating center using a secure file sharing systems or secure courier.

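### The 50% CDAS response rule sets no minimum baseline, so it cannot be evaluated at CDAS 0 and is met by one or two points at low scores, while the planned model omits baseline CDAS

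*Protocol*

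**What the plan says.** Protocol Section 8.0 makes the effectiveness of commonly used medications the primary endpoint. The clinical disease activity score is "comprised of patient pain (0-10), patient global disease activity per report (0-10), clinical lesion count by physician" and it "will be used to determine response". The threshold follows directly: ">=50% of reduction of CDAS is defined as favorable response". The score is compared "at clinical visits prior to and after starting a new medication for comparison", so the rule covers every new start and not only the first treatment. The same paragraph also says "Response to medication will be calculated based on previously described by" two cited publications.

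Nothing in Section 3.0 obliges a patient to have active disease. The imaging criterion is itself marked optional: "Presence of bone edema on STIR or T2 fat saturation sequence on MRI within 12 weeks of enrollment (optional". Section 9.0 gives the usual visit spacing at the lead site as "every 3-12 months interval after diagnosis", and says it may vary elsewhere.

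Section 11.0 plans a linear mixed-effects model that estimates mean differences between groups. It adjusts for age, gender, number of lesions and prior medication. Baseline CDAS is not listed, and neither CDAS nor the responder variable is named as the outcome.

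**The concern.** A relative-change rule treats a fall from 2 to 1 like a fall from 20 to 10. Each CDAS component can be 0, so the total can be 0, where a percentage reduction has no value. Just above 0, an ordinary fluctuation on one patient-reported item is enough for a favorable response.

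Aim 2 compares managements as chosen in practice, without randomization. If one drug is started more often at low CDAS than another, its patients are more often unclassifiable or, without any change in their disease, more often counted as responders. The two response rates could then differ although the drugs do not, and the listed adjusters would not correct for it.

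**Working it through.** **Inputs from the protocol.** Pain 0–10, patient global 0–10 and a clinical lesion count with no stated cap (Section 8.0); a threshold of 50%; no floor and no minimum absolute change. The protocol gives no measurement error, baseline distribution, expected response rate or power figure, so it has no figure of its own to reproduce.

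**Assumptions added here.** CDAS is an unweighted sum taking whole-number values. True disease does not change. Baseline and follow-up vary independently around the same true value with SD 1 to 2 points, rounded and floored at 0.

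**Step 1: points needed.** The smallest whole-number drop that meets the rule from baseline B is B − floor(B/2).

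| Baseline B | 0 | 1 | 2 | 3 | 4 | 6 | 10 | 20 |
|---|---|---|---|---|---|---|---|---|
| Drop needed | undefined (0/0) | 1 | 1 | 2 | 2 | 3 | 5 | 10 |

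**Step 2: false response.** With observed baseline B and follow-up A,

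P(false response) = Σ over b ≥ 1 of P(B = b) × P(A ≤ floor(b/2)), divided by 1 − P(B = 0).

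Worked for true CDAS 2 and SD 1:
- P(B = 0) = Φ(−1.5) = 0.067.
- P(B = 1, 2, 3, 4, ≥5) = 0.242, 0.383, 0.242, 0.061, 0.006.
- P(A ≤ 0, 1, 2) = 0.067, 0.309, 0.691.
- Sum = 0.242×0.067 + 0.383×0.309 + 0.242×0.309 + 0.061×0.691 + 0.006×0.691 = 0.255.
- 0.255 / 0.933 = 0.27.

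Simulating 400,000 pairs per scenario gives:

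| True CDAS | False response, SD 1 to 2 | Observed baseline 0, SD 1 to 2 |
|---|---|---|
| 2 | 27–43% | 7–23% |
| 3 | 14–31% | 1–11% |
| 6 | 1–11% | under 1% |
| 10 | under 2% | about 0% |

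**Step 3: a different error model.** Put the error on the items instead: SD 1.0 on pain and on global, 0.5 on lesion count. Before rounding and flooring, the total SD is √(1 + 1 + 0.25) = 1.5, inside the range above. False response is then about 31% at true CDAS 2, 21% at 3, 10% at 5, 1.6% at 8 and about 0 at 13. The pattern is the same. The models disagree only at the very bottom: at true CDAS 1 the item model gives 32–40%, while the Step 2 formula with SD 1 gives 0.333/0.691 = 48%.

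**Step 4: what this could do to a comparison.** Take two drugs with no true effect. Suppose drug X has 10 percentage points more of its starts at true CDAS 2, and drug Y has them at true CDAS 10. The gap in apparent response is 0.10 × (27% − 0%) = 2.7 points at SD 1 and about 0.10 × (43% − 2%) = 4.1 points at SD 2. The 10-point imbalance is purely illustrative.

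**Step 5: what a floor does not do.** A floor applies to the observed score, so it also admits patients whose baseline was high by chance. Take true CDAS 4, SD 1 and, only for illustration, a floor of 6. Then P(B ≥ 6) = Φ(−1.5) = 6.7%. Nearly all of these have B of 6 or 7, so the rule needs A ≤ 3, and P(A ≤ 3) = Φ(−0.5) = 31%. Regression to the mean remains in the responder analysis.

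**The case against.** The strongest reply is that evaluability for response and the handling of zero baselines usually belong in a statistical analysis plan, which may exist, and that the two cited papers may contain a minimum-activity condition. Neither can be checked here. But the protocol does not leave the rule open. It states a response definition with its threshold and scope, and as written that definition fails over part of its own range.

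A second reply is that Section 11.0 already foresees mean differences, that Section 8.0 stratifies by past course and treatment, and that lesion number is an adjuster. This stands in part: a continuous comparison is not foreign to the plan. However, baseline pain, patient global and total CDAS are not adjusted for, and the outcome is not named.

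Third, the error SD and the summed score are assumed, and the share of low-CDAS starts is unknown. That stands fully and limits the conclusion. Three stronger readings are tempting but not supported:

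- A reader might infer that the endpoint is largely noise. The protocol gives no error or baseline data, and in every scenario from true CDAS 2 upward false response is a minority, falling to under 2% at 10.
- A reader might infer that drugs started for spinal lesions begin at low CDAS. Section 2.0 says only that treatment plans were developed "for CNO patients with an NSAID-refractory course and/or with active spinal lesions". It says nothing about symptom scores in those patients.
- A reader might infer that response rates are not comparable between drugs. That requires the drugs to differ in their share of low-CDAS starts, which is not shown either way.

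**Conclusion.** The point holds in limited form. Section 8.0 fixes a relative-change rule for every new start without a floor. On a summed score it is undefined at CDAS 0 and is decided by one or two points at CDAS 1 to 4. Under the assumed SD, false response is appreciable at true CDAS 2 and 3 (27–43% and 14–31%), modest at 6 (1–11%) and negligible at 10.

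The effect on the drug comparison is conditional: it appears only if drugs differ in how often they are started at low CDAS, and its size scales with that difference. Since treatment is chosen by the physician and baseline CDAS is not in the model, the plan as written offers no protection if the difference exists. This is worth correcting before analysis; it does not show that the registry's comparison is invalid.

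**What to change.** In Section 11.0, name follow-up CDAS as the outcome of the drug comparison, use all new medication starts, and add baseline CDAS to the covariates. This is the main remedy, because it keeps zero and low baselines in the analysis and adjusts for them directly. It will not remove all confounding by the choice of drug.

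In Section 8.0, state how the three components are combined. Limit the 50% responder analysis to starts at or above a baseline CDAS that the sponsor sets in advance, or require a minimum absolute change alongside the percentage. The documents give no basis for a particular value, so the sponsor should justify the one chosen. Report by drug how many starts fall below it, with CDAS 0 counted separately. If the cited papers already contain such a condition, write it into the protocol.

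The cost is a change of wording. Baseline CDAS is already collected, and no visit or procedure is added. The responder analysis loses its low-baseline starts, which stay in the continuous model.
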